### 10.1.6. Committees Structure

Not applicable.

## 10.1.7. Dissemination of Clinical Study Data

The sponsor will register and disclose the results of clinical studies as required by law.

## 10.1.8. Data Quality Assurance

The sponsor or designee is responsible for the data management of this study, including quality checking of the data.

All participant data relating to the study will be recorded on the eCRFs unless transmitted to the sponsor (or its designee) electronically (eg, laboratory data) or paper SAE forms. The investigator is responsible for verifying data entries are complete, accurate, and verifiable by electronically signing the eCRF.

Guidance on completing eCRFs is provided on the eCRF completion document.

The investigator must permit study-related monitoring, audits, IRB/IEC review, and regulatory agency inspections and direct access to source data documents.

Study processes, study sites (including but not limited to site visits, central laboratories, vendors), the study database, and study documentation may be subject to quality assurance audits during the study by the sponsor or sponsor's designee on behalf of the sponsor. In addition, inspections may be conducted by foreign or domestic regulatory bodies at their discretion. Such audits/inspections can occur during or after the completion of the study.

Records and documents, including signed ICFs, on the conduct of this study must be retained by the investigator for 25 years after study completion unless local regulations or institutional policies require a more extended retention period. Without the sponsor's written approval, no records will be destroyed during the retention period. No records may be transferred to another location or party without written notification to the sponsor.

Monitoring details describing strategy and activities are described in a monitoring plan.

• Study monitors will perform ongoing source data verification to confirm that data entered on the eCRF by authorized site personnel are accurate, complete, and verifiable from source documents; that the safety and rights of participants are being protected; and that the study is being conducted following the currently approved protocol and any other study agreements, ICH GCP, and all applicable regulatory requirements.

### 10.1.9. Source Documents

Source documents provide evidence for the existence of the participant and substantiate the integrity of the data collected. Source documents are filed at the investigator's site.

Data entered on the eCRF that are transcribed from source documents must be consistent with the source documents or the discrepancies must be explained. The investigator may need to request previous medical records or transfer records. Also, current medical records must be available.

The definition of what constitutes source data and its origin can be found in the monitoring plan.

The investigator must maintain accurate documentation (source data) that supports the information entered on the eCRF.

The sponsor or designee will perform monitoring to confirm that data entered on the eCRF by authorized site personnel are accurate, complete, and verifiable from source documents; that the safety and rights of participants are being protected; and that the study is being conducted in accordance with the currently approved protocol and any other study agreements, ICH GCP, and all applicable regulatory requirements.

## 10.1.10. Study and Site Start and Closure

## First Act of Recruitment

The study start date is the date on which the clinical study will be open for recruitment of participants.

The first act of recruitment is the first site activated and will be the study start date.

## **Study/Site Termination**

The sponsor or designee reserves the right to close the study site or terminate the study at any time for any reason at the sole discretion of the sponsor. Study sites will be closed upon study completion. A study site is considered closed when all required documents and study supplies have been collected and a study site closure visit has been performed.

The investigator may initiate study site closure at any time, provided there is reasonable cause and sufficient notice is given in advance of the intended termination.

Reasons for the early closure of a study site by the sponsor or investigator may include but are not limited to:

- For study termination:
  - Discontinuation of further compound development
- For site termination:
  - Failure of the investigator to comply with the protocol, the requirements of the IRB/IEC or local health authorities, the sponsor's procedures, or GCP guidelines
  - Inadequate or lack of recruitment (evaluated after a reasonable amount of time) of participants by the investigator
  - Total number of participants included earlier than expected

If the study is prematurely terminated or suspended, the sponsor shall promptly inform the investigators, the IECs/IRBs, the regulatory authorities, and any CROs used in the study of the reason for termination or suspension, as specified by the applicable regulatory requirements. The investigator shall promptly inform the participant and should assure appropriate participant therapy and/or follow-up.

## **10.1.11.** Publication Policy

The results of this study may be published or presented at scientific meetings. If this is foreseen, the investigator agrees to submit all manuscripts or abstracts to the sponsor before submission. This allows the sponsor to protect proprietary information and to provide comments.

The sponsor will comply with the requirements for publication of study results. In accordance with standard editorial and ethical practice, the sponsor will generally support publication of multicenter studies only in their entirety and not as individual site data. In this case, a coordinating investigator will be designated by mutual agreement.

Authorship will be determined by mutual agreement and consistent with International Committee of Medical Journal Editors authorship requirements.

# **10.2.** Appendix 2: Clinical Laboratory Tests

The tests listed in Table 6 will be performed as described in the laboratory manual.

Protocol-specific requirements for the inclusion and exclusion of participants are detailed in Section 5.1 and Section 5.2, respectively.

Additional tests may be performed during the study as determined necessary by the investigator or required by local regulations.

Investigators must document their review of each laboratory test result.

**Table 6:** Protocol-Required Safety Laboratory Tests

Laboratory test	Parameters		
Hematology	RBC count platelet count hemoglobin hematocrit	RBC indices: MCV MCH	WBC count with differential: neutrophils eosinophils lymphocytes basophils monocytes
Serum chemistry	ALT AST albumin a BUN bilirubin (total and direct) creatinine	GFR glucose potassium sodium calcium chloride bicarbonate	total protein a creatine kinase HbA1C HDL LDL triglycerides C-reactive protein
Routine urinalysis	
 
Specific gravity
 
pH, glucose, protein, blood, ketones, bilirubin, urobilinogen, nitrite, leukocyte esterase
 
Microscopic examination (if blood or protein is abnormal)
 
Urine protein quantitative analysis (if protein is abnormal)
 
		
Pregnancy testing	Highly sensitive serum hCG pregnancy serum test at screening and urine test at other time points (as needed for WOCBP potential, defined in Section 10.4.1)		
Other tests	
 
SARS-CoV-2 nasopharyngeal swab test (PCR) (if applicable)
 
HBV, HCV, HIV (refer to exclusion criterion 4 and Sections 10.2.1.2, 10.2.1.3, and 10.2.1.4, respectively)
 
Menopausal test (FSH) if applicable (to confirm non-WOCBP status)
 
IgGa (to verify exclusion criterion 11)
 
		

<sup>a This result will be blinded postbaseline.

ALT=alanine aminotransferase; AST=aspartate aminotransferase; BUN=blood urea nitrogen; FSH=follicle-stimulating hormone; GFR=glomerular filtration rate; HbA1C=glycated hemoglobin; HBV=hepatitis B virus; hCG=human chorionic gonadotropin; HCV=hepatitis C virus; HDL=high-density lipoprotein; IgG=immunoglobulin G; LDL=low-density lipoprotein; MCH=mean corpuscular hemoglobin; MCV=mean corpuscular volume; PCR=polymerase chain reaction; RBC=red blood cell; WBC=white blood cell; WOCBP=women of childbearing potential

## **10.2.1.** Other Screening Tests

### 10.2.1.1. SARS-CoV-2

Participants will be tested for SARS-CoV-2 if they are symptomatic or if applicable law requires testing; if applicable, a negative PCR test (central or local laboratory) is required within 72 hours before enrollment and should occur regardless of a participant's vaccination status.

## 10.2.1.2. Hepatitis B Virus

Active acute or chronic HBV is exclusionary. Participants with an active acute or chronic HBV at screening will be excluded from the study.

The serologic marker combinations shown in Table 7 will be used to identify an active HBV infection.

**Table 7:** Interpretation of Hepatitis B Serological Test Results

	Test resul	lt	
HBsAg	Anti-HBc	Anti-HBs	Interpretation
Positive	Positive	Negative	An active HBV infection is exclusionary
Negative	Positive	Negative	A low-level chronic HBV infection with impaired liver function is exclusionary a

anti-HBc=total hepatitis B core antibody; anti-HBs=hepatitis B surface antibody; HBsAg=hepatitis B surface antigen; HBV=hepatitis B virus

## 10.2.1.3. Hepatitis C Virus

An active acute or chronic HCV infection is exclusionary. The HCV antibody serologic test will identify an active infection as indicated in Table 8.

**Table 8:** Interpretation of the Hepatitis C Antibody Test

HCV Ab test result	Interpretation
Positive	An active acute or chronic HCV infection is exclusionary unless an RNA test indicates HCV negative

Ab=antibody; HCV=hepatitis C virus

## 10.2.1.4. Human Immunodeficiency Virus

HIV-positive is permissible if all of the following conditions are met:

- CD4  $\geq$  200 cells/mm^3 (Table 9, Section 5.2 exclusion criterion 4.d)
- Viral load is < 200 copies/mm³ or undetectable (Table 9, Section 5.2 exclusion criterion 4.c)
- Participant is receiving stable antiretroviral therapy for at least 3 months (minimally) before screening

<sup>a This decision will be made by a medical doctor with sufficient experience in hepatology or infectious disease. Additional tests (eg, HBV viral load) could be required to determine the participant's status.

• AIDS-defining condition is absent

AIDS-defining conditions include the following:

- Cytomegalovirus retinitis with loss of vision
- Pneumocystis jiroveci pneumonia
- Chronic intestinal cryptosporidiosis
- Mycobacterium tuberculosis (pulmonary or extrapulmonary)
- HIV-related encephalopathy
- Invasive cervical cancer

**Table 9:** Interpretation of HIV Test Results

HIV test result	Clinical condition/CD4 count/ viral load	Interpretation
Positive	AIDS-defining condition is present or CD4 < 200 cells/mm 	Test results and clinical conditions or CD4 count confirm the AIDS diagnosis, which is exclusionary
Positive	Viral load > 200 copies /mm³ despite participant receiving antiretroviral therapy	Participant is ineligible because the antiretroviral therapy is not adequate
Positive	Viral load< 200 copies/mm³ but the participant is not receiving antiretroviral therapy	Participant is ineligible because not receiving antiretroviral therapy

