## 5.2. Exclusion Criteria

Participants will be excluded from the study if any of the following criteria apply:

- 1. Known autoimmune disease or any medical condition that, in the investigator's judgment, would interfere with an accurate assessment of clinical symptoms of pSS or puts the participant at undue risk
- 2. History of malignancy unless considered cured by adequate treatment with no evidence of recurrence for  $\geq 3$  years before the first administration of IMP. Adequately treated participants with the following cancers may be included at any time:
  - a. Basal cell or squamous cell skin cancer
  - b. Carcinoma in situ of the cervix
  - c. Carcinoma in situ of the breast
  - d. Incidental histological finding of prostate cancer (TNM stage T1a or T1b)
- 3. Clinically significant uncontrolled active acute or chronic bacterial, viral, or fungal infection
- 4. Positive serum test at screening for an active infection with any of the following:
  - a. HBV that is indicative of an acute or chronic infection, unless associated with a negative HBsAg or negative HBV DNA test
  - b. HCV based on HCV antibody assay unless a negative RNA test is available

- c. HIV based on test results of a CD4 count of < 200 cells/mm^3 that are associated with an AIDS-defining condition
- d. HIV based on test results of a CD4 count of ≥200 cells/mm³ not adequately treated with antiviral therapy
- 5. Clinically significant disease, recent major surgery (within 3 months of screening), or intention to have surgery during the study; or any other medical condition that, in the investigator's opinion, would confound the results of the study or put the participant at undue risk
- 6. Current participation in another interventional clinical study
- 7. Known hypersensitivity to IMP or 1 of its excipients
- 8. History (within 12 months of screening) of current alcohol, drug, or medication abuse as assessed by the investigator
- 9. Pregnant or lactating state or intention to become pregnant during the study
- 10. Previously participation in an efgartigimod clinical study and treatment with  $\geq 1$  dose of IMP
- 11. Total IgG of < 4 g/L at screening
- 12. Secondary Sjögren's syndrome overlap syndromes where another confirmed autoimmune rheumatic or systemic inflammatory condition (eg, rheumatoid arthritis, systemic lupus erythematosus, scleroderma, inflammatory bowel disease) is the primary diagnosis
- 13. Positive SARS-CoV-2 PCR test at screening

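### The HIV viral-load limit is printed per mm³, which equals 200,000 copies/mL and fits poorly with its stated use as a marker of adequate antiretroviral therapy; the sponsor should confirm the unit.

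*Protocol*

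**What the plan says.** Section 10.2.1.4 of the protocol opens with "HIV-positive is permissible if all of the following conditions are met". Four conditions follow:

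- CD4 of at least 200 cells/mm³, with a reference to exclusion criterion 4d.
- "Viral load is < 200 copies/mm³ or undetectable", with a reference to exclusion criterion 4c.
- "Participant is receiving stable antiretroviral therapy for at least 3 months (minimally) before screening".
- No AIDS-defining condition.

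Table 9 in the same section has two rows that use the viral load:

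- On therapy: "Viral load > 200 copies /mm³ despite participant receiving antiretroviral therapy", interpreted as "Participant is ineligible because the antiretroviral therapy is not adequate".
- Not on therapy: "Viral load< 200 copies/mm³ but the participant is not receiving antiretroviral therapy", which is also ineligible.

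In Section 5.2, criterion 4d reads "HIV based on test results of a CD4 count of ≥200 cells/mm³ not adequately treated with antiviral therapy". It contains no viral-load figure. Criterion 4c concerns a CD4 count below 200 cells/mm³ with an AIDS-defining condition and does not mention viral load. Table 6 in Section 10.2 sends the reader to criterion 4 and Section 10.2.1.4 for HIV. Neither the protocol nor the SAP gives a viral-load limit per mL.

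**The concern.** The limit has a job stated in the protocol: to separate participants whose antiretroviral therapy is working from those whose therapy is not. As printed, it can flag inadequate therapy only above 200,000 copies/mL. A limit that high does not sit naturally beside an undetectable load as its alternative. It also has the same number and the same volume unit as the CD4 condition directly above it, so a unit carried over from one bullet to the next is a plausible explanation.

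What is at stake is a safety threshold, not an efficacy estimate. Section 4.3 expects the chosen regimen to lower IgG by about 70%. Section 2.3.1 names serious infection as a potential clinically significant risk and lists the exclusion of uncontrolled infection as a mitigation. Section 8.4.6 makes infections events of special interest because of low IgG. Sections 5 and 8 do not allow waivers, so the printed number carries weight when a site decides on eligibility.

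**Working it through.** **Inputs**

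- Printed limit: 200 copies/mm³ (Section 10.2.1.4, viral-load condition; Table 9, both viral-load rows).
- Volume conversion: 1 mL = 1 cm³ = (10 mm)³ = 1000 mm³. This is arithmetic, not a figure from the documents.
- The documents give no derivation of the limit, so there is no calculation of theirs to reproduce.

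**Step 1: convert the printed limit**

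copies/mL = copies/mm³ × 1000

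200 × 1000 = 200,000 copies/mL

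**Step 2: compare with the same number per mL**

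This reading is an assumption used only to show the size of the discrepancy.

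200 copies/mL ÷ 1000 = 0.2 copies/mm³

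200,000 ÷ 200 = 1000, so the printed limit would be 1000 times looser.

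**Step 3: run example loads against the viral-load condition alone**

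| Load (copies/mL) | Load (copies/mm³) | Below 200 per mm³ (as printed) | Above 200 per mm³ (Table 9, on therapy) | Below 200 per mL (assumed reading) |
|---|---|---|---|---|
| 50 | 0.05 | yes | no | yes |
| 1,000 | 1 | yes | no | no |
| 10,000 | 10 | yes | no | no |
| 100,000 | 100 | yes | no | no |
| 199,999 | 199.999 | yes | no | no |
| 200,000 | 200 | no | no | no |
| 200,001 | 200.001 | no | yes | no |

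Every load up to 199,999 copies/mL meets the printed condition and escapes the Table 9 row for inadequate therapy. Loads from 200 to 199,999 copies/mL are those on which the two readings differ.

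**Step 4: see whether other text supplies or corrects the number**

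- Criterion 4d turns on whether the participant is "not adequately treated with antiviral therapy", without a figure.
- Criterion 4c, which the viral-load condition cites, contains no viral load. The reference therefore does not lead to a figure either.
- The unit is the same in all three places, so a single text-extraction slip is unlikely.

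Section 10.2.1.4 with Table 9 is therefore the only numeric definition of adequate treatment in the documents.

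**The case against.** The strongest reply is that the protocol does not contradict itself on the number. All three statements agree, no per-mL limit or laboratory reporting unit appears anywhere, and the case for a unit error is indirect. This stands in part. A reader might infer that 200 copies/mL was intended, but the documents cannot establish that. They show that the printed limit is implausible beside its own purpose, which is enough to require confirmation from the sponsor.

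A second reply is that a participant with a high load could still be kept out. This also stands. A reader might infer that people with uncontrolled HIV would be enrolled, or that every load below 200,000 copies/mL is eligible. The documents do not support that. The four conditions apply jointly, and a participant not on therapy is ineligible whatever the load. Criterion 3 (clinically significant uncontrolled infection), criterion 4d as worded, and criterion 5 (undue risk) also remain. Except for the stated conditions, these rest on judgment and do not replace a sound numeric definition.

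Two further inferences fail. A value of exactly 200 copies/mm³ is not left undecided: it fails the condition of being below 200, although Table 9 has no row for it. And a reader might expect sites to convert units differently and reach opposite decisions on the same participant. That is possible but not shown: Section 8.3.4 sends viral marker testing to a central laboratory, and the laboratory manual is not among the documents.

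**Conclusion.** The point holds as a limit that is wrong as written or, at the least, needs confirmation. The printed 200 copies/mm³ is exactly 200,000 copies/mL. That is hard to reconcile with the undetectable alternative and with Table 9's reading of a higher load on therapy. The viral-load condition also cites a criterion that says nothing about viral load.

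The conversion rests on no assumption. The factor of 1000 is conditional on the same number having been meant per mL. That a load just under 200,000 copies/mL on therapy is too high for the purpose is an inference from the section's own wording, since the documents do not define a controlled load.

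The effect is confined to the viral-load condition and to HIV-positive candidates, who are likely to be few among about 30 participants. No endpoint, estimand or sample-size figure changes. It still deserves correction, because it is a decision threshold for participant safety and the only number behind criterion 4d.

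**What to change.** The sponsor should:

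1. Check the limit and its unit against the source from which they were taken.
2. State the confirmed limit identically in the Section 10.2.1.4 condition and in both viral-load rows of Table 9, in the unit the central laboratory reports.
3. Correct the reference from the viral-load condition to criterion 4c, and point criterion 4d to the confirmed figure so that one definition decides whether treatment is adequate.

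Which limit is right is for the sponsor to establish.

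The cost is a text correction in a few places. Because it touches eligibility it belongs in a protocol amendment, which under Section 10.1.1 needs IRB/IEC approval, and health authority approval if the amendment is substantial. It can be carried with other changes.

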# 10.3. Appendix 3: AEs and SAEs: Definitions and Procedures for Recording, Evaluating, Follow-up, and Reporting

### 10.3.1. Definition of AE

#### **AE Definition**

- An AE is any untoward medical occurrence in a clinical study participant, temporally associated with the use of IMP, whether or not considered related to the IMP.
- NOTE: An AE can therefore be any unfavorable and unintended sign (including an abnormal laboratory finding), symptom, or disease (new or exacerbated) temporally associated with the use of IMP.

### Events to Be Collected as AEs

- Any abnormal laboratory test results (hematology, clinical chemistry, or urinalysis) or other safety assessments (eg, ECG, radiological scans, vital sign measurements), including those that worsen from baseline, considered clinically significant in the medical and scientific judgment of the investigator (ie, not related to progression of underlying disease)
- Exacerbation of a chronic or intermittent preexisting condition including either an increase in frequency and/or intensity of the condition
- New condition detected or diagnosed after IMP administration even though it may have been present before the start of the study
- Signs, symptoms, or the clinical sequelae of a suspected intervention-intervention interaction
- Signs, symptoms, or the clinical sequelae of a suspected overdose of either IMP or a
  concomitant medication. Overdose per se will not be reported as an AE/SAE unless it is an
  intentional overdose taken with possible suicidal/self-harming intent. Such overdoses should
  be reported regardless of sequelae.
- Lack of efficacy or failure of expected pharmacological action per se will not be reported as an AE or SAE. Such instances will be captured in the efficacy assessments. However, the signs, symptoms, and/or clinical sequelae resulting from lack of efficacy will be reported as AE or SAE if they fulfill the definition of an AE or SAE.

### Events NOT to Be Collected as AEs

- Any clinically significant abnormal laboratory findings or other abnormal safety
  assessments that are associated with the underlying disease, unless judged by the
  investigator to be more severe than expected for the participant's condition
- The disease/disorder being studied or expected progression, signs, or symptoms
  of the disease/disorder being studied, unless more severe than expected for the participant's
  condition
- Medical or surgical procedure (eg, endoscopy, appendectomy): the condition that leads to the procedure is the AE

- Situations in which an untoward medical occurrence did not occur (social and/or convenience admission to a hospital)
- Anticipated day-to-day fluctuations of preexisting disease(s) or condition(s) present or detected at the start of the study that do not worsen

